The work in Aim 1 and 2 is expected to provide sufficient preliminary data to support a future feasibility study that rigorously evaluates a faith-based storytelling intervention incorporating narratives from religious songs that address the psychological distress among patients and FCGs. The greater impact of this intervention is to reduce mental suffering and, assist the African American cancer patient and FCG to engage in supportive relationships during the diagnosis and treatment for cancer.

**1. Study Design:** The proposed feasibility study uses a quasi-experimental (pre-post test, repeated measures) design and qualitative methods to: 1) determine feasibility and acceptability, and 2) estimate effect sizes for outcomes of (psychological distress (primary outcome), spiritual well-being, patient-physician communication, supportive family relationships, and quality of life (secondary outcomes) of the Faith-Based African American Cancer Survivorship Storytelling Intervention among African American cancer patients and their FCGs. Qualitative methods will allow us to explore the influences of concepts from SCT and Transportation Theory on acceptability and satisfaction with the intervention. Specifically, we will use open-ended interviews to explore influences of identification, engagement, and emotional response to components of the intervention. A qualitative descriptive design  including content analysis  will be used to analyze data obtained from open-ended interviews.

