**2. Study setting and sample.**

**a. Setting.** The study will be implemented in partnership with the outpatient oncology unit at the Grady Cancer Center for Excellence (GCCE). The GCCE is located within the Grady Healthcare System which is a public hospital with nearly 600,000 patient visits each year. The majority of revenues generated through Medicare and Medicaid reimbursement. The Georgia Cancer Center for Excellence (GCCE) at Grady was established by the Georgia Cancer Coalition as part of an initiative to build a statewide network of people and organizations to provide exceptional cancer treatment for all Georgians. *In 2015, GCCE provided care to 1308 cancer patients (674 men/630 women).*

**b. Population to be studied:** For this feasibility study, we will recruit a total of 40 dyads with

a recent cancer diagnosis. Patient inclusion criteria captures patients (age 30-89 years) with 1) newly diagnosed with any stage cancer; 2) treatment plans to include weekly outpatient chemotherapy; 3) previously screened and with greater than 0 level of psychological distress; and, 4) willingness to participate in all study activities including data collection; 6) willing to identify a FCG (immediate or extended family member) to participate. Participants will be excluded if they have completed surgery with no plans for chemotherapy; if they find conversations around religion or spirituality emotionally upsetting; if completed more than half of prescribed chemotherapy treatments; or, in hospice care. We will also exclude participants not able to provide informed consent.

**FCG (immediate or extended family member) Inclusion Criteria are:** 1) 18 years or older; 2) able to provide informed consent; and, 3) willingness to participate in study activities including data collection. FCG's will be excluded if they find conversations around religion or spirituality emotionally upsetting.

- c. **Sample size justification:** Since this is a feasibility study, our aim will be to compute effect sizes that will guide power calculation for testing intervention effectiveness in a future RCT. Preliminary power calculation indicated that group sizes of 40 dyads (total sample 80) will achieve 80% power to detect a minimum difference of 0.6 in a repeated measurements design having a Compound symmetry covariance structure (standard deviation of 1, within subject correlation of 0.2, and an alpha level of 0.05 assumed).

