- d. **Recruitment efforts:** The success of our recruiting efforts will be dependent on developing and maintaining collaborative relationships with personnel at clinic sites. The PI has already obtained the support of GCCE Medical Director, Deputy Director, Social Worker, and Administrator. In addition, during the start-up phase of the study, we will make informal presentations about the study to center clinicians and also presentations at formal protocol start-up meetings with clinic personnel. These steps are important to introduce the study, make clinicians and staff more knowledgeable about the objectives, eligibility criteria, and logistics of the study and gain their support. We have devised a process for working with physicians and nurses and other practitioners in the clinic setting that facilitates accrual of patients into clinic studies. A major concern of clinic personnel is disruption in the flow of the clinic. The PI will meet regularly with clinic personnel to cooperate with and adhere to policies for accessing patients and to ensure that our recruiting efforts do not become burdensome for clinical staff. Clinic staff will be asked to assist with identifying patients diagnosed with a recent diagnosis of cancer. We will also review charts to confirm type cancer, stage of cancer, type and duration of planned treatment, and psychological distress screening scores.
- e. **Field Methods:** Research participants will be required to participate in intervention activities and 5 data collection interviews (1 optional open-ended interview). Interviews to complete both open-ended interviews and quantitative measures will take approximately 45 minutes. The actual administration of the intervention (viewing of video recordings) will take approximately 30 minutes with all sessions to occur over a 3-week period.

Participants will be asked to complete interviews at baseline (time of enrollment into study), after each intervention session, and at 6 weeks. These time intervals will allow us

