*Psychological distress* levels for cancer patients will be measured with the Hospital Anxiety, Depression Scale (HADS). The HADS is a 14-item self-report scale for anxiety and depressive states for patients. Internal consistency with African American oncology patients has ranged from .77 (Anxiety) and .78 (Depression). The HADS is sensitive to change after integrative therapy interventions with scores for Anxiety (8.20 $\pm$ 4.34 to 5.79 $\pm$ 3.64); Depression (5.97 $\pm$ 4.00 to 3.96 $\pm$ 3.23). Scoring for the Anxiety and Depression Subscales of the HADS is (0-21); Normal (0-7); Borderline Abnormal Case (8-10); and Abnormal Case (11-21). Patients and family caregivers will be asked to complete this evaluation at baseline and after all of the intervention sessions.

*Quantitative Assessment of narrative quality (narrative characteristics, identification, transportation)*. Assessment of narrative quality (narrative characteristics, identification, and transportation) will be examined using the Narrative Quality Assessment Tool. Narrative characteristics will be examined using a 9 item scale that measures perceived likability of characters in the story, emotional relevance of the storyline, and cultural elements of the stories. Identification will be examined using a 8-item scale that measures the degree to which participants are able to relate to the characters in the video recordings or perceive their story to be similar to their own. Transportation (engagement) will be examined using a 6-item scale

that measures participants emotional connections to the stories in the video recordings. Response options will be on a 5-pt scale and similar to that in other questionnaires in this pilot (1=not at all to 5=quite a bit). Internal consistency for the three scales range from .92 - .95 respectively. Validity was determined through hypothesized factor structures (CFA). Patients and family caregivers will be asked to complete these evaluations after each intervention session.

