**Intervention Group.** In this preliminary study, the intervention will consist of 3 weekly sessions (each session occurs over 30 minutes duration) delivered to the patient and FCG during an outpatient chemo infusion visit. In the **first step**, the RA/PI will review again purpose of the intervention and follow-up data collection. In **step two**, the patient and FCG will be given a link and password to Vimeo video sharing platform to view preselected video recordings representing the 5 categories of hymns. Immediately after each session, the RA/PI will conduct a short open-ended interview with participants to determine participant identification, engagement, and emotional response to the recordings. We will also explore experiences with use of hymns as a coping strategy. This data will assist with the further refinement of the intervention for a future RCT. In **step three**, we will schedule times for subsequent intervention and data collection sessions.

**Informed Consent Process:** The PI will read the consent form by phone or video conference platform unless participants would prefer to read it her/himself. Participants will be permitted to discuss the study with family or friends and ask the PI questions. Once the verbal consent form has been reviewed (or read to participants) the research participant will be asked to express their understanding of the consent form. Participants will be asked to describe their understanding of the study to ensure comprehension of the study. Research subjects will be given a copy of the verbal consent form for their records.

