#### **10. Plans for analysis, statistical and/or otherwise:**

- a.** Data analysis will occur on a password protected computer and data stored on servers provided by Emory University.
- b.** Specifically, we will use structured and unstructured interviews to explore influences of identification, engagement, and emotional response to the intervention. We will also explore qualitatively participant experiences with the use of hymns as a coping strategy.

Statistical software: SAS v9.3 will be used for all quantitative statistical analyses.

Quantitative descriptive analyses will be used to describe the baseline characteristics, interrater reliability, and frequencies and rankings of evaluations of video recorded narratives among study participants. The chi-square and Fisher's exact tests (cells smaller than five) will be used to determine differences in the participant responses to the video-recorded narratives according to gender (male vs. female) and patient vs. family caregiver.

Atlas.ti will be used to manage and analyze qualitative data. A qualitative descriptive design  using open-ended semi-structured interviews and qualitative content analysis  will be used to elicit and analyze patient and FCG response to transportation.

**Aim 1: Develop a series of professionally edited narrative video recordings** of African American cancer patient and FCG survivorship narratives that are grounded in the strong spiritual culture of African Americans. The recordings will be professionally edited to capture concepts of Stress and Coping Theory and include content of patient/FCGs describing the psychological stressors encountered, and faith-based strategies used to in response to the psychological distress experienced, and health outcomes. The selection of video recorded narratives for the pilot test will consist of those that capture a complete story (stressful cancer experience, faith-based coping strategy used, and health outcome) and deemed to have appropriate sound and visual quality. We will also review the final selection to ensure characters in the video recordings vary by age, gender, and type cancer.

**Aim 2: Pilot test for usability and evaluation of transportation.** A combined quantitative and qualitative methodology will be used to examine transportation of the video

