recorded narratives. For evaluation of transportation, we examine means and frequencies to scales responses for narrative quality assessment: similarity to and identification; narrative engagement; and, the emotional engagement. We will use percentiles to rank the selected video recorded narratives. Narratives with higher levels of rankings (top 50%) will be retained for future feasibility testing.

Qualitatively, data from the open-ended interview questions related to usability and evaluation of transportation identity, engagement, and emotional response will be transcribed verbatim and uploaded into Atlas.ti for analysis. Guided by principles of conventional content analysis , each participants' responses to the open-ended interviews will be organized according to categories that emerge from the data. Specifically, we will analyze interview data for *usability*: participant responses to perceived navigation (ease of use), content (video length, topics covered, presentation), persuasiveness (mood, encouragement), and value (time spent, future use, potential recommendations to others. We will also qualitatively explore interviews for transportation: similarity to and identification; narrative engagement; and, the emotional engagement of participants to selected recordings. We will use interrater reliability to validate themes emerging from the data .

Guided by principles of conventional content analysis , each participants' responses to the open-ended interviews will be organized according to categories that emerge from the data. Codes will be assigned to words or text followed by grouping and categorizing these codes into meaningful clusters. Finally, we will develop definitions for each category/theme with a table representing the definition and an exemplar for themes from the data. We anticipate that these categories will capture the characters/narrators they more frequently identify with, find similar to themselves, perceive as engaging, and elicit positive emotional response. We will also explore data for participant explanations for ranking of recordings. We will use this data to further edit the video recordings for a future feasibility test.

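### Does the 80% power statement, with no matching HADS or effect-size analysis in section 10, leave the study without its main estimate?

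*Combined protocol and SAP*

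**What the plan says.** Section 1 (Study Design) describes a pre-post, repeated-measures feasibility study. Its second purpose is to "estimate effect sizes for outcomes of (psychological distress (primary outcome"), followed by four secondary outcomes. Section 2.c gives the same purpose: "our aim will be to compute effect sizes that will guide power calculation for testing intervention effectiveness in a future RCT". It then gives the power statement: "Preliminary power calculation indicated that group sizes of 40 dyads (total sample 80) will achieve 80% power to detect a minimum difference of 0.6", assuming SD 1, within-subject correlation 0.2, compound symmetry and alpha 0.05. The outcome, the occasions compared, the sidedness and the unit (patient, caregiver or dyad) are not named.

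On timing, the HADS paragraph states: "Patients and family caregivers will be asked to complete this evaluation at baseline and after all of the intervention sessions". Section 2.e schedules interviews at baseline, "after each intervention session, and at 6 weeks". The Intervention Group paragraph says that "the intervention will consist of 3 weekly sessions".

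Section 10 (Plans for analysis) names chi-square and Fisher's exact tests "to determine differences in the participant responses to the video-recorded narratives according to gender (male vs. female) and patient vs. family caregiver". Under Aim 2, "we examine means and frequencies to scales responses for narrative quality assessment", with a percentile ranking of the videos and qualitative content analysis. It does not mention HADS change, an effect size or an interval.

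**The concern.** A power statement should describe a test that the analysis section contains. A 0.6 SD difference under compound symmetry belongs to a repeated comparison of a continuous mean. The only tests in section 10 are categorical comparisons of video ratings, so the two cannot refer to the same analysis. The term for group sizes in 2.c also reads like a two-arm calculation, whereas the protocol describes one intervention group.

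The stake would be the effect size intended for a future RCT. Read literally, section 10 does not produce it. An analyst who adds it must choose the occasion and the standardising SD after the data are in, and that choice moves the answer. The HADS anxiety figures quoted in the protocol give 0.47, 0.56 or 0.60 depending on the SD used. If one of these were carried unexamined into a two-arm calculation at 80% power, the requirement would be 71, 52 or 45 per arm.

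**Working it through.** **Inputs.** From 2.c: 40 dyads, difference 0.6, SD 1, correlation 0.2, alpha 0.05, stated power 80%. From the HADS paragraph: anxiety 8.20 (SD 4.34) to 5.79 (SD 3.64); depression 5.97 (SD 4.00) to 3.96 (SD 3.23). Assumed, because the documents do not say: two-sided testing, and 36 or 32 complete pairs for losses of 10% and 20%.

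**1. The stated 80%.** It cannot be reproduced uniquely, because the contrast and the number of measurements are not given.

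| Reading | Power for 0.6 |
|---|---|
| One group of 40, paired pre-post (t) | 83.3% |
| One group of 40, overall F test over 3 / 4 / 5 occasions (range 0.6, middle means at the midpoint) | 75.4% / 69.5% / 64.8% |
| One group of 40, baseline against the mean of 3 / 4 post measures | 94.8% / 95.9% |
| Two groups of 40, single measure (normal) | 76.5% |
| Two groups of 40, difference in change (normal) | 56.4% |
| Two groups of 40, ANCOVA, one post measure (normal) | 78.2% |
| Two groups of 20, mean of three measures (normal) | 79.3% |
| Two groups of 20, mean of two measures, one-sided (normal) | 79.0% |

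The three readings within two points of 80% (the last three rows) all need a comparison group that the protocol does not describe. Among the one-group readings the paired pre-post comparison is closest, and it is slightly above 80%.

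**2. Which reading the text favours.** The HADS paragraph places HADS at baseline and after all the sessions. The next paragraph places the narrative-quality scales after each session. The difference in wording points to one post-intervention HADS. Section 2.e schedules interviews and does not assign HADS to every one.

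**3. Power and precision on that reading.**

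SD of change = √(2 × (1 − 0.2)) = √1.6 = 1.265.

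Noncentrality = 0.6 × √n / 1.265. Half-width of the 95% interval = t(0.975, n − 1) × 1.265 / √n.

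| Complete pairs | Noncentrality | Power (t) | Half-width, SD units |
|---|---|---|---|
| 40 | 3.00 | 83.3% | 2.023 × 1.265 / 6.325 = 0.40 |
| 36 | 2.85 | 79.0% | 2.030 × 1.265 / 6.000 = 0.43 |
| 32 | 2.68 | 73.9% | 2.040 × 1.265 / 5.657 = 0.46 |

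The smallest number of pairs that gives 80% is 37.

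**4. Effect of the standardising SD.** The mean change is the same in every version: 8.20 − 5.79 = 2.41 for anxiety and 5.97 − 3.96 = 2.01 for depression.

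| Denominator | Anxiety | Depression |
|---|---|---|
| SD of change, correlation 0.2 | 2.41 / √(4.34² + 3.64² − 0.4 × 4.34 × 3.64) = 2.41 / 5.08 = 0.47 | 2.01 / 4.61 = 0.44 |
| Baseline SD | 2.41 / 4.34 = 0.56 | 2.01 / 4.00 = 0.50 |
| Pooled SD | 2.41 / √((4.34² + 3.64²) / 2) = 2.41 / 4.01 = 0.60 | 2.01 / 3.64 = 0.55 |

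At an assumed correlation of 0.5 the change-SD versions become 0.60 and 0.55. The spread therefore comes from the scale on which one change is expressed. A report giving the mean change, both SDs and the pre-post correlation lets a reader move between the versions.

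**5. Section 10 against the formal aims.** C. Goals/Aims lists two aims: develop the videos, and evaluate usability and acceptability. Effect sizes are in neither. Section 10 is organised by those aims and covers them. The gap lies between section 10 and the purposes in sections 1 and 2.c.

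**The case for a change.** The strongest case for a change is that the effect size is why the sample was sized as it was, and that a study meant to feed an RCT should fix its estimate before the data are seen. Sections 1 and 2.c state the purpose, section 10 omits it, and nothing has been redacted there. The power sentence cannot be tied to one test, and the plausible one-group readings run from 65% to 96%. A correction would cost two paragraphs and no extra data for HADS.

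The omission stands, and so does the loose wording about groups. The consequences are weaker than they look:

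- No stated rule gives a wrong result. Nothing in section 10 forbids or misdefines the HADS estimate, and the protocol states elsewhere that it will be made and from which data.
- The extreme power figures come from less natural readings. The 95% and 96% also assume that the full 0.6 is present from the first session onward.
- The 71, 52 and 45 per arm treat an uncontrolled pre-post change as the between-arm difference, so they assume no change in the control arm. They also mix denominators suited to different RCT analyses. The HADS inputs are quoted from a cited study of integrative therapies and are not data from this intervention.
- Writing in a powered paired test would commit a feasibility study to a test it may not intend. Adding at the same time that no test is planned would recreate the mismatch.

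Which contrast the authors had in mind remains unknown. Forty patients against 40 caregivers would also fit the totals, so replacing their sentence with a one-group figure would be a guess.

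**Conclusion.** The observation is correct, but it does not call for a change. The effect-size commitment is in sections 1 and 2.c, the HADS data are collected before and after the intervention, and a competent analyst would report the change with its interval and SDs. What is missing is the definition on paper: the score, the occasion and the denominator. The same detail is missing for the four secondary outcomes named in section 1.

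The sample size is not in question. On the most natural reading 40 complete pairs give 83.3% power for 0.6 SD, and the mean change is estimated to within about 0.40 SD. At 36 pairs power is 79.0%, just under the stated figure; at 32 pairs it is 73.9%, with a half-width of 0.46 SD. For a calculation that the protocol itself calls preliminary, in a feasibility study, that is tolerable.

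This rests on one post-intervention HADS, one group, two-sided 0.05, SD 1 and correlation 0.2. The loss rates are assumptions. If the authors intended an overall test across several occasions, power for 0.6 would be below 80% (75.4% for three occasions, 64.8% for five), but nothing in the documents says that they did.

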**C. Goals/Aims:** The proposed study addresses a need to integrate spirituality with cancer care as requested among African Americans from the PI's previous research . In the PI's research with African Americans, a dominant mental health promoting strategy used in response to a cancer diagnosis is the use of religious stories and songs . African Americans have a strong cultural history of relying on religious stories and songs to overcome oppression and mental suffering encountered in their lived experience . If successful, the findings from this preliminary study will contribute to the evidence that spirituality is important to cancer care and to achieving optimal patient outcomes among this medically underserved population. More importantly, the infusion of spirituality in cancer care has the potential to reduce the high levels of psychological distress experienced among African Americans and their FCG's ; to enable them to become more engaged in their cancer care  and in supportive family relationships ; and, ultimately to improve the overall quality of life for African American cancer patients and their FCGs .

**To achieve our overall goal of improving health outcomes for African American cancer patient/FCG, the following aims will be achieved:**

**Aim 1:** Develop a series of professionally edited narrative video recordings of African American cancer patient and FCG survivorship narratives that are grounded in the strong spiritual culture of African Americans. The recordings will be professionally edited to capture the essence of patient/FCGs describing the psychological stressors encountered, and spiritually-based strategies used to in response to the psychological distress experienced, and mental health outcomes.

**Aim 2:** Evaluate the usability and acceptability of this intervention. Usability is evaluated through clarity, persuasiveness, and ease of use. Acceptability will be evaluated through enrollment, participation, and concepts of Transportation Theory (identification, engagement, and emotional response).

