to identify the factors and strategies that affect health outcomes over time and serve to provide preliminary data to support a larger test of the intervention. These points will also allow for comparisons with other long-term investigations of psychological distress among cancer patients. At baseline data collection we will collect demographic characteristics of participants including age, gender, education, marital status, occupation, employment status, religious affiliation, proximity to family, type and stage of cancer, type treatment, date of diagnosis, date of treatment, and psychological distress screening scores. All data collection will be conducted by phone or video conferencing platform. There will be an 6th optional open-ended interview after the interview sessions to further explore sources of and expressions of distress among participants.

*Demographic and clinical characteristics.* For patients, we will collect data on psychological distress levels (the NCCN Distress score from patient records and the Hospital Anxiety, Depression Scale (HADS)), type and staging of cancer, and type of cancer treatment by either chart review or self-report. For patients and FCGs we will collect information on age, gender, education level, health status, religious affiliation, religiosity, insured status, income, and geographic residence. The religiosity scale measures frequency of using spiritual practices such as the use of religious songs, reading religious materials, and, attending church. Collection of data for demographic and clinical characteristics will occur immediately after obtaining informed consent and before viewing the video narratives.

*NCCN Distress Scale (National Comprehensive Cancer Network)* is a well-known screening tool for distress. In the GCC, this tool is administered to all newly diagnosed cancer patients. This screening tool is a thermometer on which patients rate their distress on a level of 0-10 with 10=extreme distress and 0=no distress. The NCCN-DT will be obtained from patient records to determine eligibility for this study. We will only recruit patients with a NCCN-DT score of  $\geq 4$  which is likely indicative of high levels of distress.

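### Case finding is described only with help from clinic staff and no eligible-patient denominator is planned, so selective referral before approach could bias the enrolment measure unseen

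*Combined protocol and SAP*

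**What the plan says.** Four statements in the protocol bear on this point.

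- **Case finding (section 2, item d, Recruitment efforts).** "Clinic staff will be asked to assist with identifying patients diagnosed with a recent diagnosis of cancer". No other way of finding patients is described.
- **Chart review (same item).** "We will also review charts to confirm type cancer, stage of cancer, type and duration of planned treatment, and psychological distress screening scores". Its stated purpose is confirmation.
- **Distress screening (section 2, item e, paragraph on the NCCN Distress Scale).** At this centre "this tool is administered to all newly diagnosed cancer patients". Also, "The NCCN-DT will be obtained from patient records to determine eligibility for this study".
- **Use of enrolment (section C, Aim 2).** "Acceptability will be evaluated through enrollment, participation, and concepts of Transportation Theory".

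Item d also says that staff will be briefed on the study, to "make clinicians and staff more knowledgeable about the objectives, eligibility criteria, and logistics of the study and gain their support", and that "A major concern of clinic personnel is disruption in the flow of the clinic".

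Nothing in the protocol describes consecutive or list-based screening, a log of patients screened, eligible, approached and declining, or the denominator over which enrolment will be expressed.

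**The concern.** An enrolment proportion informs a later trial only if one knows whom it is a proportion of. Here the people approached may already have passed through an informal filter: which recently diagnosed patients staff happened to mention. Staff will know the study's objectives and eligibility criteria, and they have a reason to limit disruption in the clinic. Uneven referral is therefore possible, though it is not described.

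A log that begins at approach would miss such a filter, because the filter acts earlier. The baseline items on religiosity, health status and stage will describe those who enrol, but the plan offers no matching information on eligible patients who were never approached.

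At stake is the enrolment component of acceptability, in a study whose stated purposes are to determine feasibility and acceptability and to guide a future RCT. The remedy lies close at hand, since the team already opens the records that hold the distress scores.

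**Working it through.** The plan states no enrolment figure, so there is nothing to reproduce. The check has two parts: a reading of the text, and an illustration of size in which every input is assumed.

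**Reading the text**

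1. Who finds patients? Staff assist, by recent diagnosis. They are not said to be the only route, nor are they asked to judge suitability.
2. What do the records do? They confirm clinical facts and determine eligibility. They are not said to generate the list of people to approach.
3. Could they do so? The distress score is said to cover all newly diagnosed patients, and planned treatment is already read from the chart.
4. Is enrolment an outcome? Yes, under Aim 2. Its denominator is not defined.

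**Size, if referral is uneven**

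Let a share q of eligible patients be more receptive, and let staff refer them r times as often as the rest. The receptive share among those referred is s = qr / (qr + 1 − q). If the two groups enrol at rates a and b, observed enrolment is s·a + (1 − s)·b, while the true rate is q·a + (1 − q)·b. With r = 1, s = q and the bias is zero.

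*Upper case: staff sort exactly on who would accept.* Take q = 0.6, a = 1, b = 0, so the true rate is 60%. Observed enrolment is 0.6r / (0.6r + 0.4):

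- r = 1.5: 0.9 / 1.3 = 69.2%, bias 9.2 points
- r = 2: 1.2 / 1.6 = 75.0%, bias 15.0 points
- r = 3: 1.8 / 2.2 = 81.8%, bias 21.8 points

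*Milder cases: receptiveness predicts acceptance imperfectly.* Take q = 0.5, so s = r / (r + 1) = 0.600, 0.667 and 0.750 for r = 1.5, 2 and 3.

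| a / b | True rate | r = 1.5 | r = 2 | r = 3 | Bias (points) |
|---|---|---|---|---|---|
| 60% / 40% | 50% | 52.0% | 53.3% | 55.0% | 2 to 5 |
| 70% / 30% | 50% | 54.0% | 56.7% | 60.0% | 4 to 10 |
| 80% / 20% | 50% | 56.0% | 60.0% | 65.0% | 6 to 15 |
| 70% / 50% | 60% | 62.0% | 63.3% | 65.0% | 2 to 5 |
| 80% / 40% | 60% | 64.0% | 66.7% | 70.0% | 4 to 10 |

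Taken together, the range is 0 (unselective referral) to about 20 points (exact sorting at r = 3), with 2 to 15 in the intermediate cases.

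**Narrative ratings**

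With q = 0.5 and an assumed gap of 0.5 to 1.0 points between the groups on the 1 to 5 scale, the mean rises by (s − 0.5) × gap: from 0.1 × 0.5 = 0.05 to 0.25 × 1.0 = 0.25 points. Section 10 keeps the narratives ranked in the top 50%. Adding the same amount to every narrative leaves their order, and so that decision, unchanged.

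**The case against.** A reader might infer that staff will act as gatekeepers who favour receptive or fitter patients, and that enrolment, ratings and baseline HADS will all be inflated as a result. The documents do not support that reading.

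- Staff only assist, and the criterion they are given is a recent diagnosis. Preference for receptive or fitter patients is an inference.
- Much of the selection on receptiveness is open and deliberate. Section 2, item b excludes people upset by religious or spiritual conversation, and requires willingness to take part and to name a family caregiver. This would remain under any screening method.
- Narratives are retained by relative rank, which a uniform shift does not alter. For baseline HADS, neither a direction nor a size of effect can be shown.
- An overstatement of 9 to 22 points holds only if staff sort exactly on who would accept. Milder assumptions give much less, and unselective referral gives none.
- The plan sets no enrolment threshold that a bias could tip, and this is a feasibility study of 40 dyads.
- The distress score alone does not establish eligibility, and item d commits the team to clinic policies on access to patients.

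All of this stands, and it limits the point to enrolment. It does not remove it. Silence about how the approach list is made means that uneven referral is neither prevented nor measurable. The open eligibility exclusions differ in kind from an upstream filter: the study team can apply and count them.

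**Conclusion.** The point holds in a limited form. Case finding is described only with staff help, the records that could provide a screening list are used to confirm and to determine eligibility, and enrolment is an acceptability measure without a denominator. Any selective referral before approach would bias the enrolment proportion and could not be detected from the data planned.

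Whether such referral will occur, and how large its effect would be, is unknown. The span of 0 to about 20 points rests on assumed referral ratios of 1 to 3, assumed acceptance rates, and enrolment being expressed as a proportion of those approached. The documents supply none of these. No change to the top-50% ranking follows from a uniform rating shift, and no effect on baseline HADS is established. This is a correctable weakness that should be dealt with before recruitment. It does not invalidate the study.

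**What to change.** In section 2, item d:

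1. Reconcile the distress criterion first. Item b admits any score above 0, while the NCCN paragraph in item e requires at least 4. A screening list cannot be built until one is stated throughout.
2. Screen newly diagnosed patients consecutively from the distress-screening records, using that criterion and the planned-chemotherapy criterion from the chart.
3. Approach listed patients in date order, within the clinic's access policies.
4. Where staff ask that a patient not be approached, record the request and its reason.
5. Log numbers screened, chart-eligible, approached, declined and enrolled. Criteria learned only at approach, such as having a willing caregiver, go in the log as reasons for non-enrolment.
6. Under Aim 2, define enrolment as the number enrolled over all chart-eligible patients, and show the intermediate counts beside it.

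The cost is some additional chart screening by the study team, which already plans to review charts, with no extra procedure for patients. The reported enrolment proportion is likely to be lower than one based on those approached, but its denominator will be known.
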